6.1.2 Descriptive analyses

Descriptive statistics for actual results, changes from baseline and percentage change from baseline will be presented by treatment and timepoint and will be repeated for the subsets of patients with tear or no tear, as well as for the subsets of patients with steroid or non-steroid use prior to treatment.

6.1.3 Statistical model, assumptions and hypotheses

The primary end-point (change from baseline in WORC score at Week 14) will be analyzed by repeated measures analysis of covariance including all WORC scores available. The change at Week 14 will be compared between treatments to address the primary objective.

The baseline WORC score will be included as a covariate. The stratification factors partial tear/no tear and previous steroid injection (yes/no) will be included in the model as fixed effects along with fixed effects for treatment, timepoint and the treatment by timepoint interaction. An unstructured within-patient covariance will be considered.

The number of covariance and mean parameters may be reduced by model comparison tools such as the BIC criterion for model fit. Missing variables will be considered missing at random.

The adjusted mean of treatment effect at Week 14 as well as the difference between treatment arms will be reported along with a 95% one-sided (90% two-sided) confidence interval.

The primary analysis will also be repeated for patients where the affected arm is the dominant arm.

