6.2 Treatment arms

Patients will be assigned to one of the following 2 treatment arms in a 1:1 ratio, with approximately 50 patients per arm.

- Group 1: Secukinumab 300 mg s.c. (2 x 150 mg)
- Group 2: Placebo s.c. (2 injections)

Treatment is administered at Day 1 (randomization visit), and Weeks 1, 2, 3, 4, 8 and 12.

Subjects who complete the assessments associated with Week 14 visit should continue the study in a (treatment free) follow up period of 10 weeks up to 24 weeks.

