11.4.1 Primary Variable(s)

The primary variable, the WORC score, will be available at Baseline and weeks 2, 4, 8, 12 and 14

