11.4.2 Statistical model, hypothesis, and method of analysis

The primary end-point (change from baseline in WORC score at Week 14) will be analyzed by repeated measures analysis of covariance including all WORC scores available. Change at Week 14 will be compared between treatments to address the primary objective. The baseline WORC score will be included as a covariate. The stratification factors partial tear/no tear and previous steroid injection (yes/no) will be included in the model as fixed effects. A 95% one-sided (90% two-sided) confidence interval for the treatment effect at Week 14 will be reported. Missing variables will be considered missing at random.

Initially, models with an unstructured within-subject covariance and a separate mean for each treatment and time point will be fitted. These models may be reduced in number of covariance and mean parameters by model comparison using tools such as the BIC criterion for model fit.

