Safety assessments will include physical examinations, ECGs, vital signs, standard clinical laboratory evaluations (hematology, blood chemistry, and urinalysis), adverse event and serious adverse event monitoring.

Figure 1-1 Study design

2 First interpretable results (FIR)

Commercially Confidential Information

3 Interim analyses

Commercially Confidential Information

4 Statistical methods: Analysis sets

For patients for which the actual treatment received does not match the randomized treatment the treatment actually received will be used for the analysis.

The safety analysis set will include all patients that received any study drug.

The PK analysis set will include all patients with at least one available valid (i.e. not flagged for exclusion) PK concentration measurement, who received any study drug and experienced no protocol deviations with relevant impact on PK data.

The PD analysis set will include all patients with any available PD data, who received any study drug and experienced no protocol deviations with relevant impact on PD data.

For efficacy data summaries and statistical analyses for the Day 127 visit, only patients who have completed the treatment Epoch will be included. For Day 169, only patients who have completed the treatment Epoch and have completed the Follow-up Epoch will be included.

The analysis sets and protocol deviation codes are related as follows:

Table 4-1 Protocol deviation codes and analysis sets

Category	Text description of deviation	Data exclusion
Deviation code		
Patients are excluded from PK analysis in case of these PDs:		
INCL01	Written informed consent was not obtained before any study assessment was performed	Exclude patient from PK analysis set Yes
Patients are excluded from PD analysis in case of these PDs:		
INCL01	Written informed consent was not obtained before any study assessment was performed	Exclude patient from PD analysis set Yes
INCL3B	Patient did not fulfil the following: Tendinopathy with no more than a 50% tear as established by ultrasound at screening (historic data acceptable if not older than 3 months) and MRI at baseline: Sein MRI tendinopathy scoring system grade I-III; with no tear or partial tear [maximum 50% tendon thickness (Bauer tendon thickness score maximum 2); AP length maximum 10 mm (Bauer tendon length score max 2)]. Maximum 50% of patients with partial tear	Exclude patient from PD analysis set

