6.1.1 Variable

The primary variable, the WORC score, will be available at pre-dose, day 1 and weeks 2, 4, 8, 12, 14, 18 and 24. The total score and the subscores will be included in the summaries and statistical analyses detailed in the following sections and will take the form of percentage of normal scores derived as:

- Physical symptoms score = (600-sum of Physical symptoms answers)/6
- Sports and Recreation score = (400-sum of Sports and Recreation answers)/4
- Work score = (400-sum of Work answers)/4
- Lifestyle score = (400-sum of Lifestyle answers)/4
- Emotions score = (300-sum of Emotions answers)/3
- Total score = (2100-sum of all answers)/21

If there are <=2 missing values in a domain, the domain score can be calculated using the average of the other items in the domain. If there are more than 2 missing items in a domain, the concerning WORC questionnaire is considered incomplete and is excluded from the analyses.

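### The primary model's mean terms may be cut by BIC with none protected, so the reported Week 14 difference can become one effect shared by all visits

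*SAP*

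**What the plan says.** The primary analysis is a repeated-measures analysis of covariance of change from baseline in WORC score, aimed at the treatment difference at Week 14. SAP 6.1.3 includes baseline score, the two stratification factors and "fixed effects for treatment, timepoint and the treatment by timepoint interaction", with an unstructured covariance. It then states: "The number of covariance and mean parameters may be reduced by model comparison tools such as the BIC criterion for model fit". On reporting it says: "The adjusted mean of treatment effect at Week 14 as well as the difference between treatment arms will be reported", with a 90% two-sided interval.

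Protocol 11.4.2, repeated in the protocol summary, starts from a separate mean for each treatment at each time point and continues: "These models may be reduced in number of covariance and mean parameters by model comparison".

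Neither document names a term that must stay, lists candidate models, sets an order of reduction, or says which N enters BIC. Protocol 11.4.5 plans no sensitivity analysis.

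The set of visits is also unsettled. Protocol 11.4.1 says the WORC score "will be available at Baseline and weeks 2, 4, 8, 12 and 14", which is five post-baseline visits. SAP 6.1.1 says it "will be available at pre-dose, day 1 and weeks 2, 4, 8, 12, 14, 18 and 24", which is seven. The last two fall in a period in which patients "should continue the study in a (treatment free) follow up period of 10 weeks up to 24 weeks" (protocol 6.2).

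**The concern.** Protocol 3.2 justifies Week 14 as the time by which the final Week 12 injection can have acted, so earlier visits are not regarded as equivalent to it. A model without treatment-by-timepoint treats them as equivalent: its fitted treatment difference is identical at all visits. The estimate, interval and test for the primary objective would then describe something other than the Week 14 effect, under the same label.

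The error can go either way. An effect that builds up is underestimated and may be missed. An early effect that has worn off can be reported as a Week 14 benefit. The choice would be made on treatment-coded data, because fitting the interaction needs the codes, and no unreduced result is guaranteed beside it.

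**Working it through.** **1. The plan's own figure.** Protocol 11.7 uses a difference of 20, an SD of 34 (22 × √(14/6) = 33.6), 40 completers per arm and a one-sided 5% test. The standardised difference is (20/34) × √(40/2) = 2.63, and power is Φ(2.63 − 1.645) = 83.8% (83.2% with the t distribution). This agrees with the stated power above 80%. It is the power of the Week 14 contrast alone.

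**2. What BIC requires.** Comparing separate visit effects with one common effect, BIC keeps the interaction only if the likelihood-ratio statistic exceeds (visits − 1) × ln N.
- Five visits, N = 80: 4 × 4.38 = 17.5 (chi-square p = 0.0015).
- Seven visits, N = 80: 6 × 4.38 = 26.3 (p = 0.0002).
- N = 100: 18.4 (p = 0.0010) and 27.6 (p = 0.0001).
- If N counts observations (400 for five visits), the five-visit threshold rises to 24.0.

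**3. What the reduced model estimates.** With visit differences d and covariance S, the common effect is (1′S⁻¹d)/(1′S⁻¹1). Take an effect rising linearly to 20 at Week 14: 2.9, 5.7, 11.4, 17.1 and 20 at Weeks 2, 4, 8, 12 and 14. With constant variance and equal correlation, each visit has weight 0.20 and the shared effect is 57.1/5 = 11.4. For an early effect of 15, 15, 15, 5 and 0, it is 50/5 = 10, although the true Week 14 effect is zero.

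**4. Simulation.** The documents give no effect profile or visit correlation, so these are assumed. Settings: 40 per arm, SD 34 at Week 14, complete data, no covariates, maximum likelihood with unstructured covariance, 3,000 trials per case, and BIC choosing between the full model and one common effect. Constant variance: equal correlation 0.6, or 0.93 to the power of weeks apart. Growing variance (proportional to time): independent increments, the same with 30% visit noise, or equal correlation 0.6. Entries are five visits / seven visits.

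| True effect | Variance | Interaction dropped | Mean reported Week 14 estimate | 90% CI coverage | One-sided rejection |
|---|---|---|---|---|---|
| Linear to 20 at Week 14, then held | constant | 77–94% / 82–99% | 12.1–14.2 / 13.4–15.2 | 60–66% / 64–72% | 58–66% / 74–76% |
| Same | growing | 74–90% / 91–98% | 5.6–6.9 / 2.0–4.6 | 6–21% / 1–6% | 30–46% / 13–43% |
| 15 to Week 8, 5 at Week 12, then 0 | constant | 81–90% / 80–98% | 7.3–7.4 / 5.5–6.7 | – | 36–40% / 30–37% |
| Same | growing | 77–89% / 90–96% | 10.3–12.8 / 13.6–16.4 | – | 78–89% / 90–96% |

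The full model has 82–85% power and 89–91% coverage for the linear profile, and 4–6% rejection for the early one.

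**5. Cases with little or no harm.** With a constant effect of 20, the mean estimate is 19.9–20.2 and power 92–100%. Under a global null, rejection is 5.5–6.8%. Adding a linear treatment-by-time trend as a third candidate reduces the harm. For the linear profile, the estimate is then 16.4–19.3 / 8.9–15.6, coverage 57–83% / 37–78% and power 73–86% / 57–80%. For the early profile, false benefit is 19–58% / 23–70%. Null rejection becomes 6.3–8.2%.

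**The case against.** The strongest reply is that the step is optional and removing the interaction is its least natural use. SAP 6.1.3 says the interaction is included and that the Week 14 change is compared. WORC change at the other visits is a set of separate secondary variables (protocol 11.5, SAP 6.2.1), and a common effect would make those treatment comparisons redundant. By-visit summaries and plots (SAP 6.1.2 and 6.1.3.2) would expose a discrepancy at Week 14. This makes a sensible outcome more likely but does not require it: a reduced model still yields a Week 14 difference, and the descriptive output does not replace the primary contrast.

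Two points on size stand:
- **Growing variance.** These rows rest on extreme weights. Independent increments put all the weight on Week 2. Growing variance with equal correlation gives 0.99, 0.26, −0.03, −0.10 and −0.12 for five visits, which is not an average in the ordinary sense. Protocol 11.7 uses growing variability to extrapolate an SD conservatively; it does not set out a covariance model. The conclusion should not lean on these rows.
- **Seven visits.** This model is the less likely one. Protocol 6.4 provides a database lock for the Week 14 primary analysis, and SAP section 4 says: "For efficacy data summaries and statistical analyses for the Day 127 visit, only patients who have completed the treatment Epoch will be included". Day 169 is restricted further, so Weeks 18 and 24 may be fitted separately. Only visits in the same fitted model share the estimate.

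The simulation also omits baseline, strata and missing data. This is a Phase II trial, and the harm needs three things together: the option is used, the interaction is what goes, and the effect varies over visits.

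**Conclusion.** The concern holds. Both documents permit a data-driven reduction that can change what the primary analysis estimates, and nothing in them exempts treatment-by-timepoint. That the shared effect replaces the Week 14 contrast once the term is dropped is algebra and needs no assumption. That BIC would often drop it in a trial of this size follows from the thresholds of 17.5 and 26.3.

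The size of the harm is illustrative. The fairest guide is five visits with constant variance and a common effect as the only alternative: about 6 to 8 points lost from a true 20 and power of 58–66% when the effect builds linearly, or 36–40% false benefit when an early effect has gone. If the effect is constant over visits there is no bias and power rises.

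**What to change.** In SAP 6.1.3, protocol 11.4.2 and the protocol summary, replace the reduction sentence with wording such as:

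> Treatment, timepoint and treatment-by-timepoint are retained in the primary model whatever the model-fit criteria show, and the Week 14 contrast is taken from that model. Only the covariance structure may be simplified, by a pre-specified rule (for example, a fixed fallback order if the unstructured covariance does not converge).

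In the same place, name the visits in the model, so that the five in protocol 11.4.1 and the seven in SAP 6.1.1 are reconciled.

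The cost is wording in three places and 4 to 6 more mean parameters than a common-effect model, with 80 to 100 patients. The full model had 82–85% power at the planned effect in the simulation, in line with protocol 11.7. What is given up is the extra power of pooling when the effect is constant (92–100%) or plateaus early. With 10 at Week 2 and 20 thereafter, BIC selection gave 81–99% power, but with a mean estimate of 11.6–18.6 against a true 20.

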6.1.3.1 Model checking procedures

Residual plots will be produced to assess the adequacy of the models.

6.1.3.2 Graphical presentation of results

Data will be presented graphically using mean (SE) plots and repeated for the subsets of patients with tear or no tear, as well as for the subsets of patients with steroid or non-steroid use prior to treatment.

6.2 Secondary Objectives

6.2.1 Variables

Secondary variables include:

- Change from baseline in WORC score at weeks 2, 4, 8, 12, 18 and 24.
- Disability of Arm, Shoulder and Hand Questionnaire (QuickDASH) score at weeks 2, 4, 8, 12, 14, 18 and 24 (where available in local language/dialect).
- American Shoulder and Elbow Surgeons Shoulder Evaluation Form (ASES) score at weeks 2, 4, 8, 12, 14, 18 and 24
- EQ5D-5L your health today and index scores (see Appendix 1 for SAS code) at weeks 2, 4, 8, 12, 14, 18 and 24
- Pain score using a VAS scale (considering the last 24 hours) at weeks 2, 4, 8, 12, 14, 18 and 24
- Patient global assessment (PGA) score of disease activity, using a VAS scale (considering the last 24 hours), at weeks 2, 4, 8, 12, 14, 18 and 24
- Physician global assessment (PhGA) score of disease activity, using a VAS scale (considering the last 24 hours), at weeks 2, 4, 8, 12, 14, 18 and 24
- MRI Sein score at weeks 8, 14 and 24

6.2.2 Derivations and analysis considerations for secondary variables

Baseline is defined as day 1 or if data is missing at day 1 then the last non-missing predose value will be used as the baseline.

Quickdash

At least 10 of the 11 items must be completed for a score to be calculated. The assigned values for all completed responses are summed and averaged, producing a score out of five. This value is then transformed to a score out of 100 by subtracting one and multiplying by 25.

This transformation is done to make the score easier to compare to other measures scaled on a 0-100 scale. A higher score indicates greater disability.

ASES

The shoulder score is derived by the following formula:

$(10 - \text{Visual analog scale pain score}) \times 5 + (5/3) \times \text{Cumulative activities of daily living score.}$

Pain VAS

For Pain VAS the result from the site visit where the assessment date matches the actual visit date will be used in the summaries and analyses. If the result from the site is not available then the result from the diary data where the assessment date matches the actual visit will be used.

Sein Scores

The following rules will be applied for selection of the appropriate result for the descriptive statistics and statistical analyses:

- If an adjudicated result is present then it should be used as the result for that timepoint.
- If there are 2 results present that match then there was no need for an adjudicated result and either result can be used for the analysis, by default the first one will be used.
- If there is only 1 result available then this single result will be used in the analysis.

6.2.3 Descriptive analyses

Descriptive statistics will be presented by treatment and timepoint for actual results, changes from baseline and percentage change from baseline. A frequency table and a shift table will be provided for Sein scores. Summaries will also be presented by affected/unaffected arm/dominant/non-dominant arm as appropriate for selected endpoints.

For Pain VAS the descriptive statistics will be repeated for the subsets of patients with tear or no tear, as well as for the subsets of patients with steroid or non-steroid use prior to treatment.

6.2.4 Statistical model, assumptions and hypotheses

The secondary variables (except for the Sein score) will be summarized descriptively and analyzed similar to the primary analysis.

The secondary variable Sein MRI score at weeks 14 and 24 will be analyzed by ordinal categorical regression. A model with an additive treatment effect on the cumulative logistic scale will be used, and the common treatment effect estimated and reported together with 90% asymptotic two-sided confidence intervals. Baseline SEIN score will be included as a covariate and the stratification factors, partial tear/no tear and previous steroid injection (yes/no) will be included in the model as fixed effects.

All the secondary analyses will also be repeated for patients where the affected arm is the dominant arm.

6.2.4.1 Model checking procedures

Residual plots will be produced to assess the adequacy of the models.

6.2.4.2 Graphical presentation of results

Data will be presented graphically as mean (SE) profiles (apart from Sein scores). Graphical presentation of Sein scores using a barchart will be provided to highlight changes over time.

For Pain VAS the mean (SE) profiles will be repeated for the subsets of patients with tear or no tear, as well as for the subsets of patients with steroid or non-steroid use prior to treatment

6.3 Exploratory objectives

6.3.1 Variables

Commercially Confidential Information

6.3.2 Derivations and analysis considerations for exploratory variables

Commercially Confidential Information

6.3.3 Descriptive analyses

Commercially Confidential Information

Commercially Confidential Information

7 Statistical methods for safety and tolerability data

7.1 Variables

Adverse events, serious adverse events, vital signs (blood pressure, pulse rate, body temperature), height and body weight, ECG evaluations, laboratory measurements (haematology, clinical chemistry, lipid panel, glucose, urinalysis, immunogenicity), tuberculosis screening, chest X-ray, ultrasound, local tolerability (injection site reactions), pregnancy testing, assessment of fertility, as well as patient demographics, baseline characteristics, patient examination, and treatment information.

7.2 Descriptive analyses

Patient demographics and other baseline characteristics

All data for background and demographic variables will be listed by treatment group and patient. Summary statistics will be provided by treatment group.

Relevant medical history, current medical conditions, results of laboratory screens, drug tests and any other relevant information will be listed by treatment group and patient.

Treatment

Data for study drug administration and concomitant therapies (including rescue medication) will be listed by treatment group and patient.

Vital signs

All vital signs data will be listed by treatment, patient, and visit/time and if ranges are available abnormalities (and relevant orthostatic changes) will be flagged. Summary statistics will be provided by treatment and visit/time.

ECG evaluations

All ECG data will be listed by treatment, patient and visit/time, abnormalities will be flagged. Summary statistics will be provided by treatment and visit/time.

Clinical laboratory evaluations

All laboratory data will be listed by treatment, patient, and visit/time and if normal ranges are available abnormalities will be flagged. A separate listing is provided presenting all parameters in a patient with any abnormal values. Summary statistics will be provided by treatment and visit/time.

Serum chemistries will include sodium, potassium, BUN/urea, bicarbonate, calcium, phosphorous, total protein, calcium, albumin, uric acid, creatinine, CK, total bilirubin, AST (SGOT), ALT (SGPT), GGT and alkaline phosphatase, at all timepoints specified in the Assessment schedule.

If the total bilirubin concentration is increased above 1.5 times the upper limit of normal, direct and indirect reacting bilirubin should be differentiated.

Triiodothyronine (T3), thyroxine (T4), thyroid-stimulating hormone (TSH), Rheumatoid factor (RF), anti-cyclic citrullinated peptide (anti-CCP) antibodies, and interferon-gamma release test done only at screening. FSH is only done at screening and only in patients who are reported post-menopausal at screening.

Adverse events

All information obtained on adverse events will be displayed by treatment group and patient. The number and percentage of patient s with adverse events will be tabulated by body system and preferred term with a breakdown by treatment. A patient with multiple adverse events within a body system is only counted once towards the total of this body system.

Adverse event reporting for Clinical Trial Safety Disclosure (CTSD)

For the legal requirements of ClinicalTrials.gov and EudraCT, two required tables, 1) on treatment emergent adverse events which are not serious adverse events with an incidence greater than 0% and 2) on treatment emergent serious adverse events and SAE suspected to be related to study treatment, will be provided by system organ class and preferred term on the safety set population. These tables will be produced by Novartis.

The summary will be done by treatment i.e. active (AIN457) or Placebo.

If for a same patient, several consecutive AEs (irrespective of study treatment causality, seriousness and severity) occurred with the same SOC and PT:

- a single occurrence will be counted if there is ≤ 1 day gap between the end date of the preceding AE and the start date of the consecutive AE
- more than one occurrence will be counted if there is > 1 day gap between the end date of the preceding AE and the start date of the consecutive AE.

For occurrence, the presence of at least one SAE / SAE suspected to be related to study treatment / non SAE has to be checked in a block e.g., among AE's in a ≤ 1 day gap block, if at least one SAE is occurring, then one occurrence is calculated for that SAE.

The number of deaths resulting from SAEs suspected to be related to study treatment and SAEs irrespective of study treatment relationship will be provided by SOC and PT.

Pregnancy test

All pregnancy test results for pre-menopausal women who are not surgically sterile will be listed by treatment, patient and visit/time.

Tolerability of investigational treatments

Tolerability will be assessed by adverse events, laboratory values, injection site reaction and immunogenicity. The local tolerability at the site of s.c. injection of the study treatment will

be assessed in case of any local reaction, until this has disappeared. The assessment of pain, redness, swelling, induration, haemorrhage and itching will be recorded, capturing AEs, including the severity (mild, moderate, severe) and the duration of the adverse reaction. Data will be listed and summarized by treatment group.

Immunogenicity

All immunogenicity results for AIN patients will be listed by treatment, patient and visit/time.

